## **8.0 Treatment Modifications**

8.1 Hepatic Toxicity: Subjects will be evaluated for symptoms and signs of RILD or other toxicity. It is expected that a proportion of subjects will have transient elevation of liver enzymes during treatment. Repeat of all Grade 4 LFTs is required within 5-10 days following the first abnormal lab value to determine if the Grade 4 levels are transient (defined here as <10 days) or persistent. Subjects exhibiting hepatic toxicity  $\geq$  5-20x baseline LFT's will be evaluated with radiological imaging procedures to assess whether change in LFTs are due to tumor progression or treatment toxicity. Subjects whose progressive liver function abnormalities while under treatment are deemed due to tumor progression will stop all protocol treatment and will be managed and followed per physician standard of care. Subjects with treatment induced hepatic toxicity of greater than 20x baseline elevation will not receive further protocol treatment unless and until liver function tests have returned to less than 5x subjects baseline value. Subjects will be evaluated for symptoms and signs of RILD or other toxicity per the schedule described in the protocol or more frequently depending on the clinical judgment of the treating team. If recovery of hepatic function requires an interruption of treatment of more than 30 days, patients will be withdrawn from the study.

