##### 4.4.3 Radiation Schedule

**4.4.3.1** SBRT will be delivered in five total fractions. The entire treatment must be delivered within 15 total days.

4.4.3.2 Three dimensional treatment planning will be used for all subjects. Volumes of tumor and normal liver will be determined, and DVH based treatment planning will be carried out, targeted to the tumor only.

4.4.3.3 Radiation Prescription Dose: The goal is to use the highest allowable prescription dose to the primary target while respecting normal tissue constraints. Dose prescription is based on the volume of normal tissues irradiated (correlated with mean liver dose) as well as proximity of stomach, duodenum, small and large bowel (GI luminal structures) to the target volumes. In the absence of adjacent GI luminal structures that may limit dose, the PTV dose prescription should be based on mean liver dose (MLD is the mean dose to the liver minus GTV's). See table below.

The dose to multiple PTVs within the same subject may vary. Conformality of the prescription dose and the 30Gy isodose lines are planning goals.

For CTP A: 27.5 Gy - 50 Gy in 5 fractions

For CTP B: 27.5 Gy - 40 Gy in 5 fractions.

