## 7.0 Study Calendars

**Table 2: Study Calendar for SBRT (Arm A)**

Active Treatment-SBRT	Pre-Rx Eval  (screening)	SBRT fractions (5 in 2 week period) 	Last fraction of treatment (prior to discharge)	2 Week Follow up post treatment (+/- 3 days)
History and Physical Exam	X			X
Weight	X			X
CBC with differential	X 			X
AST, ALT, Alk Phos, Total Bilirubin, Albumin	X 			X
Na, BUN/Creatinine	X 			X
INR	X 			X

AFP (for HCC)	X 			
Toxicity Notation	X		X	X
Multiphasic MRI or CT of the abdomen within 4-6 weeks prior to enrollment	X			
Chest CT or Chest x-ray within 1 year prior to enrollment	X			
MELD-Na, ALBI, and CTP assessment	X 			X
HRQL 	X	X 	X	X
Randomization 	X			
Simulation	X			
Treatment: SBRT 		X (over a two week period)		

 Within 2 weeks prior to randomization unless otherwise specified

 If multiple lab results are available within the screening period, use the most recent results before randomization.

 If calculations are performed multiple times, use the most recent value before randomization

 HRQL questionnaire: FACT-Hep

 Randomization may occur after all screening procedures are complete and eligibility has been met. See section 3.0 for more details.

Initial treatment should be scheduled within 3 weeks of randomization.

See section 6.0 for details on HRQL administration timelines.

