**Table 3: Study Calendar for TACE (Arm B)**

Active Treatment – TACE					
	Pre-Rx Eval  (screening)	Initial TACE	2 week Follow up post initial TACE (+/- 3 days)	Second and Following TACE treatments	2 week Follow up post TACE (+/-3 days)
History and Physical Exam	X	X	X (per MD SOC only)	X	X (per MD SOC only)
Weight	X	X	X	X	X
CBC with differential	X 	X 	X	X 	X
AST, ALT, Alk Phos, Bilirubin, Albumin	X 	X 	X	X 	X
Na, BUN/Creatinine	X 	X 	X	X 	X
INR	X 	X 	X	X 	X
AFP (for HCC)	X 	X 		X 	
Toxicity Notation	X	X	X	X	X
MRI or CT of the abdomen within 4-6 weeks prior to enrollment	X				

Chest CT or chest x-ray within 1 year prior to enrollment	X				
MELD-Na ALBI, and CTP assessment	X 		X		X
HRQL 	X	X 	X	X 	X
Randomization 	X				
Treatment:TACE 		X		X	

 Within 2 weeks prior to randomization unless otherwise specified.

 If multiple lab results are available within the screening period, use the most recent results before randomization.

 If calculations are performed multiple times, use the most recent value before randomization.

 HRQL questionnaire: FACT-Hep

 See section 6.0 for details on HRQL administration timelines.

 Randomization may occur after all screening procedures are complete and eligibility has been met. Initial treatment should begin within 3 weeks of randomization. See section 3.0 for details on randomization.

 If required labs were performed within 3 days of a TACE procedure, they do not have to be repeated unless requested by treating physician.

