### **10.3 Possible long term toxicities after SBRT:**

- Gastric or Bowel injury (ulceration, bleeding, perforation, fistula formation, or obstruction)
- Biliary obstruction due to inflammation or sclerosis
- Liver abscess
- Hepatic subcapsular injury
- Decreased renal function.
- Rib fracture
- Myositis
- Radiation-induced liver disease (RILD) including potentially fatal liver injury.
- In subjects who have Grade 4 elevation of liver enzymes levels and/or in subjects with early nonspecific signs or symptoms of liver injury, close follow-up is recommended with repeat blood work. If no tumor progression is documented in these subjects, liver injury will be presumed to be treatment related.

Only grade  $\geq 2$  toxicities will be considered in the statistical analysis. The following toxicities will require subjects to be removed from protocol treatment if the protocol treatment has not yet been completed. Patients will be followed per physician standard of care.

- Grade  $\geq 4$  hepatic toxicity for changes in AST, ALT, alkaline phosphatase, or platelet counts attributed to treatment and not attributable to disease progression. Transient grade 4 (less than 10 days) hepatic toxicities are acceptable.
- Grade  $\geq 4$  Upper GI bleeding (**attributed to treatment**, and not attributable to disease progression).
- Death due to any cause.

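### In the SBRT arm no scheduled lab can trigger the hepatic hold (8.1) or the lab-based removal rule (10.3), because Table 2 has no labs during treatment

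*Combined protocol and SAP*

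**What the plan says.** **The rules.** Section 8.1 expects some liver enzyme rises during treatment. It asks for a repeat of Grade 4 liver tests after 5 to 10 days, and for imaging when values reach 5 to 20 times baseline. Its hold reads: "Subjects with treatment induced hepatic toxicity of greater than 20x baseline elevation will not receive further protocol treatment", until values are below five times baseline. A recovery that interrupts treatment for more than 30 days leads to withdrawal from the study. Section 10.3 lists removal triggers, among them treatment-related Grade 4 or higher AST, ALT, alkaline phosphatase or platelet changes that are not transient. It limits them in time: "The following toxicities will require subjects to be removed from protocol treatment if the protocol treatment has not yet been completed".

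**The calendars.** In Table 2 (SBRT), the row "AST, ALT, Alk Phos, Total Bilirubin, Albumin" is marked at screening and at the 2-week post-treatment visit only. The CBC, renal and INR rows have the same pattern. The columns for the fractions and for the last fraction are blank for all of them. Section 4.4.3.1 gives five fractions and adds: "The entire treatment must be delivered within 15 total days".

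In Table 3 (TACE), the row "AST, ALT, Alk Phos, Bilirubin, Albumin" is marked at screening, at the initial TACE, 2 weeks after it, at every further TACE, and 2 weeks after each of those. A footnote relaxes only the timing: "If required labs were performed within 3 days of a TACE procedure, they do not have to be repeated". Table 4 gives both arms the same labs from month 3 to month 24.

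**The analysis.** Section 17.2.3 compares any toxicity by chi-square and the number of toxicities by t-test. The paragraphs on safety measures and adverse events compare labs and adverse events between arms. None of these takes account of how often labs were drawn. Section 12.3.1 counts abnormal laboratory findings as adverse events.

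**The concern.** A rule that holds or stops treatment on a lab value needs that value while treatment is still being given. In the SBRT arm the first scheduled value after baseline arrives when all five fractions have been delivered, so nothing is left to hold or stop. Whether a patient comes under either rule then depends on whether someone orders an unscheduled test, and that can differ between sites and clinicians. These are patient safety rules, and the calendar that sites follow does not supply the data they use.

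The second consequence is analytic. Comparing toxicity is a secondary objective. If one arm has more scheduled blood draws during treatment, laboratory events have more chances to be recorded there, and an unadjusted comparison may partly reflect sampling.

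**Working it through.** **1. The plan's own toxicity figure.** Section 17.2.3 states that 98 patients per arm give 99% and 95% probability of seeing at least one toxicity at true per-patient risks of 0.05 and 0.03. The formula is 1 − (1 − p)^98. At p = 0.05 it gives 0.9934 and at p = 0.03 it gives 0.9495, so both figures reproduce. The point below disputes no number in the plan, and sample size and power are unaffected.

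**2. SBRT timing.** The last fraction falls within 15 days of the start. The next scheduled panel is 14 ± 3 days later, that is, 11 to 17 days after the last fraction. Scheduled panels between first and last fraction: 0.

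**3. TACE timing.** Section 5.4 allows k = 1, 2 or 3 procedures as initial therapy, about 4 to 6 weeks apart, so the 2-week panel precedes the next procedure. Each procedure carries two panels.

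| Scheduled treatment-phase panels | SBRT | TACE k=1 | k=2 | k=3 |
|---|---|---|---|---|
| All after randomization (TACE: 2k) | 1 | 2 | 4 | 6 |
| After first exposure, leaving out the panel at the first TACE (2k − 1) | 1 | 1 | 3 | 5 |
| After the first and up to the last treatment (2(k − 1)) | 0 | 0 | 2 | 4 |

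The second row is the fair one for toxicity, since the panel at the first TACE may precede exposure. The third row shows when a scheduled value can still affect remaining treatment: never in SBRT, and in TACE only when there is more than one procedure.

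**4. Rule by rule in the SBRT arm.**
- Hold above 20 times baseline (8.1): needs treatment still to come, so it has no scheduled trigger.
- Lab-based removal (10.3): applies only before completion, so it has no scheduled trigger.
- Repeat of Grade 4 tests and imaging at 5 to 20 times baseline (8.1): neither is confined to the treatment period, so both can act on the 2-week panel.
- Upper GI bleeding (10.3) and Grade 4 events in any organ (8.2): neither depends on calendar labs alone.

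**5. Interruption limit.** Section 8.1 withdraws a patient only after more than 30 days of interruption, whereas 4.4.3.1 limits the whole SBRT course to 15 days. An SBRT interruption of 16 to 30 days stays within the first limit and breaks the second.

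**6. How far sampling could matter: an illustration only.** Assume that each panel has the same, independent chance p of showing a new event. The documents give no value for p. The chance of at least one recorded event over m panels is 1 − (1 − p)^m.
- p = 2%: SBRT 2.0%; TACE 2.0%, 5.9% and 9.6% for one, two and three procedures.
- p = 5%: SBRT 5.0%; TACE 5.0%, 14.3% and 22.6%.
- p = 2% with the eight Table 4 panels (24 / 3 = 8) added to both arms, so m = 9, and 9, 11 or 13: SBRT 16.6%; TACE 16.6%, 19.9% and 23.1%.

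For three procedures against SBRT, the ratio falls from 9.6 / 2.0 = 4.8 to 23.1 / 16.6 = 1.4 once follow-up is counted. Independence pushes all these figures towards the upper end.

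**The case against.** Section 8.1 lets the treating team evaluate patients more often than the calendar requires, and Table 2 has toxicity notation at the last fraction. An unscheduled draw can therefore trigger either rule. This stands. A reader might infer from the blank cells that the rules cannot operate in the SBRT arm, and the documents do not support that. What they show is that a mandatory rule depends on optional testing.

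Section 8.1 also covers both arms, and a removal rule conditional on unfinished treatment may simply be reached rarely in a course of at most 15 days. That is fair, and it means the passages do not contradict each other outright. But 10.3 places the removal list under an SBRT heading, and 8.1 expects enzyme rises during treatment, so the plan evidently means these rules to be usable there.

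On sampling, a reader might infer that the toxicity comparison is biased towards SBRT by a known amount. The documents do not support that either. Counts after exposure tie at 1 to 1 for a single TACE, follow-up is the same in both arms, the distribution of TACE courses is not given, and part of any excess is real toxicity from repeat treatment.

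Nor should the main comparison be restricted to common time points. Up to three TACEs are the assigned initial therapy, so dropping labs after the first or second would hide real toxicity of the control arm.

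**Conclusion.** The point holds in a limited form. As scheduled, the SBRT arm has no panel between first and last fraction, so the hold in 8.1 and the lab-based removal in 10.3 rest there on unscheduled, clinically prompted testing. Table 3 supplies scheduled values in TACE whenever more than one procedure is given. This follows from reading the calendars and needs no assumption. The 30-day and 15-day limits also need reconciling for SBRT.

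The sampling point is secondary. The scheduled counts, 1 against 1, 3 or 5, are firm. Their effect on recorded toxicity is not: the percentages above depend on an assumed p, on independence between draws, and on how many patients have more than one TACE. They show that an effect is possible in multi-course TACE; they do not estimate it.

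**What to change.** 1. Reconcile Table 2 with 8.1 and 10.3. Either the SBRT calendar carries the labs these rules act on, or the rules state how, and on what data, they apply to SBRT. In the same amendment, reconcile the 30-day interruption limit in 8.1 with the 15-day course limit in 4.4.3.1. The sponsor's clinicians decide the content. The cost is an amendment to the calendar and wording and, if labs are added, routine blood draws at visits that patients already attend.

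2. In 17.2.3 and the safety paragraphs, keep the all-data toxicity comparison as the main one. Add a sensitivity analysis of lab values and lab-based adverse events restricted to screening, 2 weeks after the last initial treatment, and months 3 to 24. It needs a rule for a panel that fits two windows. With treatment starting 0 to 3 weeks after randomization and three TACEs 4 to 6 weeks apart, the last post-treatment panel falls at about 0 + 2×4 + 2 = 10 to 3 + 2×6 + 2 = 17 weeks, which overlaps the month-3 visit and its 4-week margin. The cost is a little more analysis work and no new data.

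3. Report the number of TACE procedures and of lab panels per patient by arm, so that readers can judge how far sampling differed.

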### **5.2 Super-selective chemoembolization**

5.2.1 Once vascular supply of the tumor is identified super-selective chemoembolization of the tumor supplying artery is performed with catheter positioned in second or third order side branches. If the anatomy is sufficiently visualized with fluoroscopy, and a cone-beam CT is available, a cone-beam CT will be performed to assess appropriate segmental contrast distribution covering the target.

5.2.2 TACE will be performed with (see Appendix C). Two vials of beads will be prepared with, per the discretion of the treating physician, 50mg of Doxorubicin. Iodine contrast will be mixed

according to manufacturer guidelines and used to guide the delivery. Bead size will be at the discretion of the treating physician.

5.2.3 TACE without doxorubicin will be performed in an identical manner. Bead size will be at the discretion of the treating physician.

5.2.3 Target area will be embolized until segmental arterial stasis is achieved. In the presence of multifocal disease selective catheter positioning will be repeated for each lesion.

5.2.4 If available, final cone-beam CT will be performed to document distribution of the embolic material.

5.3 Following the TACE procedure all subjects will remain in hospital per standard of care for extended recovery.

5.4 If stasis of arterial flow to the tumor(s) was not achieved, additional TACE treatments will be administered, each approximately 4-6 weeks after the prior TACE procedure was performed until stasis is achieved with a maximum of three TACEs administered as initial therapy. After the first TACE, any additional treatments will be performed per the discretion of the treating Interventional Radiology Team.

**Completed treatment will be defined by the date of the final TACE procedure considered as part of initial therapy (up to 3 TACE treatments).**

5.5 Progression of disease will be confirmed with imaging done greater than 8 weeks from last treatment date. Images collected per transplant protocol within the 8 weeks of treatment will be repeated, as per study schematic, to confirm response to treatment or progression.

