### **8.2 Other Toxicity**

The occurrence of **treatment-related** Grade 4 adverse events in any organ system will prompt discontinuance of protocol therapy while appropriate physical examination, laboratory, and imaging assessments are undertaken per each institution's standard of care. Protocol treatment will not be resumed in the absence of recovery from adverse events of this magnitude. Once recovery to  $\leq$  grade 2 has occurred, treatment may continue at the discretion of the treating physician.

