## **12.0 Criteria for Discontinuation of Protocol Treatment**

### **12.1 Off-Treatment Conditions**

- Unacceptable toxicity as defined in section 10.
- Therapy may be discontinued prematurely at any time by subject request without prejudice to subsequent care.
- Subjects may be removed from the treatment at any time per investigator discretion.

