### **12.2 Off Study Conditions**

- Subjects will be removed if they are unable to receive either SBRT or TACE due to decompensation prior to initial therapy.
- Subjects may be removed from the study at any time by subject request.
- Subjects who go on to receive additional non-radiation therapy (i.e., treatment that is not TACE or SBRT related) will be followed for progression within the treated lesion(s). They will no longer receive protocol-directed treatment or testing.
- Subjects who develop extra-hepatic tumor will not be followed and will be censored from the data analysis.
- Subjects who undergo a liver transplant will be considered off study and will not be followed from that time point (except to determine 60-day post transplantation survival status).
- Subjects permanently removed from Liver Transplant list and will not be followed.

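### Section 8.1 takes patients off study, not only off treatment, after a hepatic interruption of more than 30 days; later safety, survival and lesion data are lost for a few patients, with little effect on the primary result

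*Combined protocol and SAP*

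**What the plan says.** Section 8.1 holds protocol treatment for treatment-induced hepatic toxicity above 20 times baseline until liver tests are below 5 times baseline. It then adds: "If recovery of hepatic function requires an interruption of treatment of more than 30 days, patients will be withdrawn from the study".

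The other toxicity rules stop treatment only:

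- **8.2** (treatment-related Grade 4 events in any organ system): "Protocol treatment will not be resumed in the absence of recovery from adverse events of this magnitude". It says nothing about leaving the study.
- **10.3** (Grade 4 or higher hepatic toxicity or upper GI bleeding, attributed to treatment): "The following toxicities will require subjects to be removed from protocol treatment if the protocol treatment has not yet been completed". It continues: "Patients will be followed per physician standard of care".
- **12.1** puts toxicity among the off-treatment conditions: "Unacceptable toxicity as defined in section 10".
- **12.2**, the separate off-study list, has no item for toxicity once treatment has begun. Its nearest entry is "Subjects will be removed if they are unable to receive either SBRT or TACE due to decompensation prior to initial therapy".

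On the analysis side, 13.1 censors a patient without a known event at the last date on study. Section 17.1 counts death as an event in the primary analysis, and 17.2.3 analyses toxicity and overall survival.

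**The concern.** The protocol separates stopping treatment (12.1) from leaving the study (12.2). For prolonged hepatic injury, 8.1 goes straight to the second. Stopping treatment protects the patient; ending observation adds no protection and discards information on the harm.

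Three things are at stake. First, Table 4 labs, liver scores, survival status and imaging stop in patients with a prolonged treatment-related liver injury, in a trial that has toxicity as a secondary endpoint. Second, the patient is censored for a reason plausibly related to outcome, in an analysis where death is an event. Third, the censoring is likely to be unequal between arms. Sites could also differ, because a patient with persistent Grade 4 transaminases and a TACE session pending can meet both 10.3 (off treatment) and 8.1 (off study).

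**Working it through.** **1. Which arm the rule reaches.** SBRT must be delivered within 15 days (4.4.3.1). TACE may take up to three sessions about 4–6 weeks apart (5.4), so up to two gaps, or 8–12 weeks, in which a session can be pending. That the rule falls mainly on TACE is an inference from these schedules; neither document states it.

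**2. When withdrawal would fall.** Section 8.1 does not say when an interruption starts. Count it from the missed session:

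- Missed session: day 28–42 after the last TACE. Withdrawal 31 days later: day 59–73.
- First TACE is within 21 days of randomization (Table 3, footnote 6). Hold after TACE #1: day 59 to 21 + 73 = 94 from randomization.
- Hold after TACE #2: 28 + 59 = 87 to 21 + 42 + 73 = 136.
- First scan window: 91 ± 28 = day 63–119 (Table 4), or 122 ± 28 = day 94–150 for unlisted patients (11.1.3.4).

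Withdrawal therefore falls around the first scheduled scan. An unlisted patient held after TACE #1 leaves no later than the day that window opens.

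**3. How many visits are lost.** Table 4 has eight quarterly visits to 24 months, but a patient who reaches the endpoint goes off study (5.6). Take the plan's TACE median of 134 days and visits every 91.3 days. Expected visits attended are the sum over k = 0 to 7 of exp(−ln 2 × 91.3k / 134). The ratio between successive terms is 0.624, so the sum is (1 − 0.624⁸) / (1 − 0.624) ≈ 2.6. If the hazard triples from day 30 (assumed), it is about 1.4. Transplant, delisting and dropout reduce it further. Hence about one to three visits per affected patient.

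**4. How many patients.** No rate is given. Assume 30–60% of TACE patients await another session and 2–5% of those are held for more than 30 days:

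- 98 × 0.30 × 0.02 = 0.6
- 98 × 0.60 × 0.05 = 2.9

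For scale, the plan's 15% yearly exponential dropout, with 365–730 days of follow-up, already implies about 7 TACE and 10 SBRT dropouts before an event.

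**5. Power.** Schoenfeld: power = Φ(|ln HR| × √(events/4) − 1.96). The plan's own case, HR 0.6 with 120 events, gives Φ(0.5108 × 5.477 − 1.96) = 79.9%, matching its 80%. If every withdrawn patient would have had an event:

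| Events | Power |
|---|---|
| 120 | 79.9% |
| 120 − 0.6 = 119.4 | 79.7% |
| 120 − 2.9 = 117.1 | 78.9% |

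**6. Bias.** Simulation with 98 per arm, TACE median 134 days, HR 0.6, events seen only at scans every 91.3 days, and a Cox model with Efron ties. Injured TACE patients have three times the hazard from day 30 (assumed) and leave at day 68. There were 10,000 trials per case:

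| Injured TACE patients | HR, kept on study | HR, withdrawn | Change in power |
|---|---|---|---|
| 1 | 0.599 | 0.602 | −0.7 points |
| 3 | 0.590 | 0.601 | −2.5 points |

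With the hazard unchanged, the shift is 0.003 or less. The simulation yields about 151 events rather than 120, so only its differences are used. Withdrawal removes TACE events and moves the estimate toward 1, against SBRT.

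**The case against.** **The contrast between sections is softer than it looks.** Section 10.3, and 8.1's own sentence on abnormalities due to tumor progression, send patients to standard-of-care follow-up, not to Table 4. Section 8.2 promises no schedule. This stands: the other rules stop treatment only, but they do not guarantee protocol follow-up. That is why the fix also touches 10.3. A reader might infer that 8.1 contradicts 12.2. It does not; 12.2 omits this reason, and the 8.1 and 10.3 triggers only overlap.

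**Section 12.2 is only a partial precedent.** It keeps following patients given other non-radiation therapy for progression in the treated lesions. A reader might take this as support for full follow-up after protocol treatment. The same bullet ends study-directed tests for them, so it supports lesion follow-up only.

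**There are other exits.** Section 5.4 leaves sessions after the first TACE to the interventional radiology team, who may end initial therapy so that arguably nothing is interrupted. Section 10.3 may take a patient with non-transient Grade 4 toxicity off treatment well before 30 days accrue. Both stand, and they make zero affected patients possible.

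**Timing against 5.5.** That section states: "Progression of disease will be confirmed with imaging done greater than 8 weeks from last treatment date". A reader might infer that patients leave before this 56-day mark. That needs the interruption to be counted from the 2-week lab visit, which gives day 42–48 after the last TACE. Since the next session is itself due on day 28–42, day 42 could involve no delay at all. Counted from the missed session, withdrawal comes 3–17 days after the mark.

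**Some data are kept.** The index event and the withdrawal are reported, as are deaths within 30 days of the end of study visits (12.4.4).

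**Conclusion.** The point holds as a cheap improvement. Section 8.1 literally ends study participation where the other toxicity rules end only treatment, and 13.1 then censors for a treatment-related harm, mainly in the TACE arm. What is lost is later liver-safety, survival and treated-lesion data.

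The size is small: about 0 to 3 of 98 TACE patients and one to three visits each. This rests on the assumed rates above, on the plan's 134-day TACE median and on counting the interruption from the missed session.

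Two stronger readings are not supported. A reader might infer from Table 4 that seven or eight of the eight visits are lost; that assumes every patient would otherwise stay 24 months, which 5.6, transplant and delisting rule out for most. A reader might also suspect that the rule helps SBRT; if the injury raises the event hazard, the bias runs toward no difference. The effect on the primary hazard ratio and power is slight under any of the assumptions tried.

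**What to change.** In the last sentence of 8.1, replace *withdrawn from the study* with *taken off protocol treatment and kept on study, with Table 4 follow-up until the primary endpoint, a 12.2 off-study condition, or 24 months*, in both arms. In 10.3, give the same follow-up to surviving patients removed from treatment for the listed hepatic or upper GI bleeding toxicities; the entry for death stays outside it. Leave the 8.1 sentence on tumor progression as it is.

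The cost is a wording amendment and a few extra follow-up visits, some in patients not on the transplant list. The sample size does not change. Recovery of data is partial: transplant, permanent delisting and the other 12.2 conditions still end follow-up, and 12.3.2 still stops adverse event reporting after another liver-directed therapy or chemotherapy.
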